### 10.3.2 Study visits

#### 10.3.2.1 Blood draw (investigation of TBE antibody persistence)

**Visit 1:** 38 months  $\pm$  60 days after the booster vaccination in Study 700401ii.

All subjects who were administered the first booster vaccination in Study 700401 will be invited for this visit. Subjects with relatively low TBE serum antibody levels (as described further) will proceed to Visit 4 (Booster vaccination) and Visit 5 (Post-booster Visit), as applicable (see [Figure 20.1-1](#), [Supplement 20.1](#)).

**Visit 2:** 46 months  $\pm$  30 days after the booster vaccination in Study 700401.

This visit will only be applicable for those subjects who have not yet received the second booster vaccination. Subjects with relatively low TBE serum antibody levels will proceed to Visit 4 and Visit 5 (see [Figure 20.1-1](#), [Supplement 20.1](#)).

**Visit 3:** 58 months  $\pm$  30 days after the booster vaccination in Study 700401.

This visit will only be applicable for those subjects who have not yet received the second booster vaccination. Subjects with relatively low TBE serum antibody levels will proceed to Visit 4 and Visit 5 (see [Figure 20.1-1](#), [Supplement 20.1](#)).

**Visit 6:** 70 months  $\pm$  30 days after the booster vaccination in Study 700401.

**Visit 7:** 82 months  $\pm$  30 days after the booster vaccination in Study 700401.

**Visit 8:** 94 months  $\pm$  30 days after the booster vaccination in Study 700401.

**Visit 9:** 106 months  $\pm$  30 days after the booster vaccination in Study 700401.

**Visit 10:** 118 months  $\pm$  30 days after the booster vaccination in Study 700401.

These additional blood draw visits are only applicable for subjects who have not yet received the second booster vaccination. Subjects with relatively low TBE serum antibody levels will proceed to Visit 4 and Visit 5 (see [Figure 20.1-2](#), [Supplement 20.1](#)).

---

ii The 29 subjects who were administered the first booster vaccination at the 4 year time point in Study 700401 and who will enter the current study in 2010 will have their Visit 1 at 34 months  $\pm$  60 days. For Visit 2 and Visit 3 the schedule is to be followed as described in the protocol.

The following assessments will be performed:

- Verification of the signed and dated informed consent/assent of the subject prior to any procedures being done (at Visit 1 ONLY);
- Inclusion and exclusion criteria (see Section 9.1 and Section 9.2);

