4.4. Other Analysis Sets

4.4.1. mITT Population

All enrolled subjects who have assay results (ELISA or NT) available at any blood sampling visit in this study will be included in the modified intent-to-treat (mITT) population. This analysis set is for the immunogenicity analysis purpose. This population will be used as the secondary analysis population for other immunogenicity objectives. All available assay results will be included in this analysis set.

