5.2. General Methods

5.2.1. Methods to Manage Missing Data

In general, only subjects with available data will be included in the statistical analysis.

Missing values for antibody titer at 38 and 46 months will neither be replaced nor estimated. Any missing values at later time points (ie, 58, 70, 82, 94, 106 and 118 months) due to early withdrawal or second booster vaccination within this current study, will be estimated if at least three data points are available, assuming an exponential decline in antibody titers in time (calculated as described in [Section 5.2.2.1](#)).

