5.2.2. Analyses for Continuous Data

5.2.2.1. Annual Decline Rate of Antibody Response

To calculate the annual decline rate of antibody response on NT, the NT titers measured at each blood sampling time point (including Study 700401 post-booster Visit, and Study B9371021 visits 1, 2, 3, 6, 7, 8, 9, 10) will be logarithmically transformed. These log transformed data will be used as dependent variable, with days after first booster dose (from study 700401) as independent variable, to calculate the annual decline rate, using regression model for each subject. The slope from the model multiplied by 365 is considered as the estimated annual decline rate for each subject. Summary statistics on the estimated annual decline across all subjects will then be presented.

Subjects with missing assay data at 38-month and 46-month after the first booster dose will not be included in this analysis. In addition, subjects with a more than 4-fold increase in TBE antibodies between successive visits will be excluded from the analysis.

Calculation of the decline rate:

- Perform linear regression of the log transformed results for each subjects;
- Annual decline rate=slope of regression line * 365;
- Calculate descriptive statistics for the annual decline rate across all subjects.

A similar analysis will be performed for the ELISA data.

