5.2.3. Analyses for Binary Data

All of the binary endpoints will be descriptively summarized along with the exact 2-sided 95% confidence interval (or Clopper-Pearson confidence limit) for the proportion. The exact confidence interval for proportion will be computed using the F distribution. If r equals the number of responses and n equals the number of subjects, then it follows that $p = r / n$ is the estimate of the proportion of responses. An exact 95% confidence interval can be computed by solving the following 2 equations. For the lower limit p_L , use:

$$p_L = \frac{rF_L}{(rF_L + (n - r + 1))} \text{ and for the upper limit } p_U, \text{ use } p_U = \frac{(r + 1)F_U}{(n - r) + (r + 1)F_U}$$

where F_L is the quantile from the F distribution for $\alpha=0.025$, with numerator degrees of freedom equal to $2r$ and denominator degrees of freedom equal to $2(n-r+1)$. F_U is the quantile from the F distribution for $\alpha=0.975$, with numerator degrees of freedom equal to $2(r+1)$ and denominator degrees of freedom equal to $2(n-r)$. When r equals 0, F_L should be set equal to 1.0 so p_L equals 0. When r equals n , F_U should be set equal to 1.0 so p_U equals 1. The confidence interval using the F distribution is described in Collett (1991¹) and implemented in SAS procedure (ie, PROC FREQ).

To estimate the seropositivity rate as determined by NT from approximate 3 years to 10 years after the first booster vaccination (from precedent study 700401), the proportion of subjects with $NT \geq 10$ at each blood sampling time point (including extrapolated from regression model for subjects with booster dose or early withdrawals from [Section 5.2.2.1](#), and the available assay results) after the first booster will be summarized with the exact 95% CI. Similarly, the proportion of subjects with $ELISA > 126$ at each blood sampling time point (including extrapolated results) after the first booster will be summarized with the exact 95% CI. The analysis will be applied to '[Per Protocol](#)' Analysis Set. For [mITT Population](#), which will include all available NT titers and ELISA concentrations, ie, no extrapolation from regression model will be done for subjects with booster dose or early withdrawals.

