6. ANALYSES AND SUMMARIES

6.1. Analysis of Primary Immunogenicity Endpoints

The primary analysis for the primary objective will be based on the evaluable immunogenicity population for the primary endpoints. 95% exact confidence intervals (CIs) will be presented along with the seropositive rate on NT as described in [Section 5.2.3](#). Missing values handling were described in [Section 5.2.1](#).

Additional analysis on the primary endpoints will also be applied to the mITT population.

P-values from the logistic regression will be presented to assess the relation of seropositive rate with the covariates (per-protocol population only).

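### From Month 46 the observed-only mITT rates and GMTs/GMCs leave out subjects boosted for low antibody, so they overstate cohort persistence; the per-protocol figures share part of the omission

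*SAP*

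**What the plan says.** **Who is bled.** Protocol 10.3.2.1 says of each of Visits 2 and 3 (Months 46 and 58): "This visit will only be applicable for those subjects who have not yet received the second booster vaccination". For Visits 6 to 10 (Months 70 to 118): "These additional blood draw visits are only applicable for subjects who have not yet received the second booster vaccination". SAP 2.2.2 gives the invitation rule for the second booster: an NT titre of 20 or less, an ELISA value of 126 VIE U/ml or less, or both. Seropositivity is NT of at least 10 (SAP 3.1.1).

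**mITT.** SAP 4.4.1: "All available assay results will be included in this analysis set". SAP 5.2.2.2 (GMTs/GMCs) and 5.2.3 (rates) both add that "no extrapolation from regression model will be done for subjects with booster dose or early withdrawals". SAP 6.1: "Additional analysis on the primary endpoints will also be applied to the mITT population".

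**Per-protocol (the primary population).** SAP 5.2.1: "Missing values for antibody titer at 38 and 46 months will neither be replaced nor estimated". From Month 58, a value missing because of a second booster or early withdrawal "will be estimated if at least three data points are available". The points entering the regression are listed in SAP 5.2.2.1: "including Study 700401 post-booster Visit, and Study B9371021 visits 1, 2, 3, 6, 7, 8, 9, 10".

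**The concern.** Whether a subject stays in the mITT denominator after Month 38 depends on that subject's own earlier antibody result. The invitation threshold (NT 20) lies above the seropositivity cut-off (NT 10). A subject who accepts therefore usually leaves before, or at, the first seronegative draw and is never again counted as negative. A rate built this way stays high almost regardless of what happens in the cohort.

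Protocol 6.6.2 says the results should help identify the best booster interval. An unlabelled ten-year rate taken only from people who never needed a booster could mislead on exactly that question. There is a second trap. Both populations lose the lowest early responders, so close agreement between the mITT and per-protocol figures could be read as support for the extrapolation, and it would not be.

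**Working it through.** **1. The plan's own decline figures.** Protocol 7.1 gives mean annual declines of -0.50, -0.38 and -0.46 and says a titre of 20 falls in a year to 12.2, 13.6 and 12.6. On natural logs, 20 × exp(-0.50) = 12.13, 20 × exp(-0.38) = 13.68 and 20 × exp(-0.46) = 12.63, which agree within rounding of the slopes. Base-10 logs would give 6.3, 8.3 and 6.9. The scale is natural log. These slopes were measured after the primary series, not after a booster.

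**2. Points available under the SAP rules.**

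| Boosted after | Usable points | Month 46 | Month 58 onward, per-protocol |
|---|---|---|---|
| Month 38 (Visit 1) | 700401 post-booster, Month 38 = 2 | missing, never estimated | never extrapolated |
| Month 46 (Visit 2) | 3 | observed | extrapolated |
| Month 58 or later | 4 or more | observed | observed, then extrapolated |

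At Month 46 the two populations have the same gap. From Month 58 the mITT analysis loses every boosted subject, and the per-protocol analysis loses those boosted after Visit 1. Month 38 is unaffected.

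**3. A bound that needs no titre model.** If a share f of the cohort is unobserved and the observed rate is p, the cohort rate lies between (1-f)p and (1-f)p + f. With p = 99%: f = 5% gives 94.1-99.1%, f = 10% gives 89.1-99.1%, and f = 20% gives 79.2-99.2%. The documents do not give f.

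**4. Size under assumptions.** The documents give no titre distribution and no decline after the first booster. Assumed: Month-38 GMT 60, 120 or 250; SD of ln titre 0.9; slope SD 0.15 per year; assay SD 0.35; NT trigger only; 175 subjects (Protocol 13.1); log-linear decline. Per-protocol values come from per-subject regressions with at least three points; the SAP's exclusion for more than 4-fold rises is not modelled.

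Share at or below 20 at Month 38: Φ[(ln 20 - ln GMT)/√(0.9² + 0.35²)], denominator 0.966, gives about 12.8%, 3.2% and 0.45%. Times 175, that is about 22, 6 and 1 subjects. With full uptake, these are also the subjects who fail the three-point rule.

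Month 46, full uptake, declines 0.10-0.50: gap 0.0-5.2 points, the same for mITT and per-protocol.

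Month 118, full uptake, NT seropositivity (%):

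| Decline per year | GMT at Month 38 | Cohort | mITT | Per-protocol |
|---|---|---|---|---|
| 0.10 | 60 | 79.2 | 99.5 | 82.5 |
| 0.10 | 120 | 90.5 | 99.6 | 90.6 |
| 0.10 | 250 | 96.7 | 99.7 | 96.5 |
| 0.20 | 60 | 63.1 | 98.7 | 66.9 |
| 0.20 | 120 | 79.7 | 98.9 | 79.8 |
| 0.20 | 250 | 91.3 | 99.2 | 90.7 |
| 0.46 | 60 | 18.0 | 92.9 | 19.2 |
| 0.46 | 120 | 33.9 | 93.5 | 33.0 |
| 0.46 | 250 | 54.5 | 94.6 | 52.6 |

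The mITT gap is 3.0-35.6 points for declines of 0.10-0.20, 17.1-53.0 at 0.30, and 27.7-78.0 at 0.38-0.50. The mITT GMT is 1.2-3.3 times the cohort GMT at 0.10-0.20 and 2.3-11 times at 0.38-0.50.

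**5. Sensitivity of the mITT gap at Month 118.**
- Incomplete uptake (80% or 60% accept each offer, or 20% or 40% always decline): 1.8-34.5 points at 0.10-0.20 and 7.9-67.6 at 0.38-0.50.
- Slope SD 0-0.05: 0.4-31.1 at 0.10-0.20.
- ELISA trigger added (GMC 600-1200, correlation 0.3-0.7): 3.2-36.3 at 0.10-0.20 and 43.4-77.8 at 0.46.
- Only subjects with NT 10-20 accept and those below 10 always decline: 2.9-28.2 at 0.10-0.20 and 24.8-33.3 at 0.46.
- A separate model (GMT 100-300, log SD 1.0, decline 0.15-0.46, slope SD 0.08, residual SD 0.3, uptake 70-100%): 1.8-46.8 points; Month 46, 0.1-1.7.

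The mITT gap was not negative in any run.

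**6. Per-protocol at Month 118.** With log-linear decline the gap is -2.1 to +3.9 points at full uptake, and up to +6.9 with slope SD 0-0.05. If the post-booster ln titre sits 1-2 above the line, because the early fall is faster, it becomes -2.4 to -13.2. The late per-protocol direction is therefore not fixed.

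**The case against.** The primary analysis is per-protocol, and from Month 58 it extrapolates for most boosted subjects. The mITT analysis is additional, and SAP 1 records that version 1.1 deliberately updated its method. Showing observed data beside model-based data is a reasonable pairing. The ingredients are also in the text: SAP 5.2.1 names the second booster as a cause of missing values, leaves Month 46 unestimated and states the three-point rule. Some counts are planned. SAP 6.4.1 tabulates blood draws per visit and numbers eligible and vaccinated, and post-booster results are shown by year. Table shells are prepared separately (SAP 2) and were not available, so a footnote cannot be ruled out. The largest gaps need a low assumed GMT, a post-primary decline rate and full uptake, although subjects are only invited. At Month 46 the gap lies within the 5.8-point confidence limit distance in Protocol 13.1. The added time-to-threshold estimate is not a protocol endpoint, and an interim analysis through five years has already been done (SAP 7).

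Much of this stands. It limits the weight of the point, and the size remains assumed. It does not remove the point. Nothing in the SAP says that the mITT rates are conditional on not yet being boosted, or that they do not estimate cohort persistence. The planned counts do not split per-protocol values into observed, extrapolated and excluded. The SAP does not claim that agreement would validate the extrapolation; the concern is that readers may infer it.

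**Conclusion.** The concern holds and should be fixed. The mechanism, the first affected visit (Month 46) and the partial overlap with per-protocol follow from the documents. The upward mITT direction follows from selection on low titre and held in every scenario tested. The size rests on assumed titres, decline and uptake: small at Month 46, possibly large by Month 118. Across the base-model runs with full uptake, the Month-118 mITT rate stays at about 91-100% while the cohort rate runs from 13% to 97%, so it says little about cohort persistence; the 13% end needs the lowest GMT and the fastest decline. For per-protocol, the omission is certain, the Month-46 effect is upward and equal to that for mITT, and the net late error may go either way. Early withdrawals are also left unextrapolated in mITT, with unknown direction.

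**What to change.** Amend SAP 5.2.1, 5.2.2.2, 5.2.3 and 6.1.

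1. Keep the mITT rates and GMTs/GMCs, but label those after Month 38 *among subjects not yet boosted*, with the number observed at each visit. State that they do not estimate cohort persistence and that agreement with per-protocol does not validate the extrapolation.
2. Give the per-protocol Month-46 figures the same label. From Month 58, show for each visit the numbers observed, extrapolated, and excluded because boosted with fewer than three points.
3. Add, over all mITT subjects, a supplementary interval-censored (Turnbull) estimate of time to the first draw meeting the existing NT and/or ELISA threshold, using actual draw dates and counting the event whether or not a booster follows. Censor at the last draw both withdrawals and subjects boosted without meeting the threshold (SAP 6.4.4.3). State that it is visit-defined, so assay variation can produce a crossing, and that it assumes non-informative withdrawal.

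Item 3 is a conservative lower bound on NT seropositivity, not an estimate of it: a subject never at or below 20 through Month 118 is above 20, hence at least 10, at that visit. In the assumed model the proportion never at or below 20 was 36.7-89.2% at declines of 0.10-0.20 and 4.5-47.8% at 0.38-0.50, below the cohort rate in every run. A booster given under the rule cannot precede the first low draw, so uptake does not affect it. Random withdrawal of 3% per interval changed it by at most 0.1 point; 9% withdrawal after NT of 40 or less raised it by 0.9-2.7 points, still below the cohort rate.

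Cost: SAP wording, three counts per visit and one standard procedure, with no new data. The downside is slightly more analysis work and less favourable supplementary figures. SAP version 1.1 is dated March 2017 and planned completion is June 2017. The documents give no date for database closure, but on those dates the change could precede it.

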6. ANALYSES AND SUMMARIES

6.1. Analysis of Primary Immunogenicity Endpoints

The primary analysis for the primary objective will be based on the evaluable immunogenicity population for the primary endpoints. 95% exact confidence intervals (CIs) will be presented along with the seropositive rate on NT as described in [Section 5.2.3](#). Missing values handling were described in [Section 5.2.1](#).

Additional analysis on the primary endpoints will also be applied to the mITT population.

P-values from the logistic regression will be presented to assess the relation of seropositive rate with the covariates (per-protocol population only).

6.2. Analysis of Secondary Endpoints

The seropositive rate on ELISA will be analyzed similar to NT. If no subject had ELISA seronegative, the logistic regression will not be applied.

All of the GMCs, GMTs, GMFRs will be summarized for the per-protocol population and for the mITT population.

RCDC will only be presented for the per-protocol population.

6.3. Analysis of Safety Data

All AE data will be summarized with count and percentages.

6.4. Analyses of Study Conduct

6.4.1. Subject Disposition, Vaccination Administration, Blood Samples

The number and percentage of subjects who are enrolled (or consented), completed the study, are qualified in each analysis population, withdrew, and with major protocol violations (excluded from per-protocol immunogenicity population), will be summarized. The reasons for withdrawal will also be tabulated. The total number of subjects with blood drawn and subjects who complied with the visit window at each visit will also be summarized.

Similarly, for subjects who are eligible for a booster vaccination, the number and percentage of subjects who are vaccinated, and with a postbooster blood draw within the protocol-specified time frame will be tabulated.

The [Full Analysis Set](#) will be used to generate these tables.

The protocol violators will also be listed.

6.4.2. Demographic, Medical History, and Baseline Characteristics

Demographic summaries will include age (at consent or age at second booster), gender, height, weight, and BMI. BMI will be derived as a ratio of body weight in kilograms (kg) to the square of the body height in meters(m) and rounded to 2 decimal points and the unit of BMI is kg/m².

These summaries may also be generated for different analysis sets.

Medical history and physical examinations performed will be summarized among all enrolled subjects at each visit as well as for any visit. Additionally, the medical history, vital signs, physical exam, and pregnancy test evaluated before the booster vaccination will all be listed among subjects who received booster vaccination.

6.4.3. Nonstudy Vaccination and Concomitant Medication

The data will be listed.

6.4.4. Protocol Deviations

The following describes any protocol deviations that relate to the statistical analyses or populations:

6.4.4.1. Deviations Assessed Prior to Enrollment

Any subjects who do not meet the inclusion / exclusion criteria will not be included in the per-protocol immunogenicity population.

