### **6.3 Population to be Studied**

A total of 202 healthy children, adolescents and young adults of both genders who participated in Study 700401 and received the first booster vaccination with either FSME-IMMUN 0.25 ml Junior or FSME-IMMUN 0.5 ml at 3 or 4 years after the third vaccination will comprise the subject population of the study.

The majority of subjects will be enrolled in the current study in late spring 2009 at approximately 38 months after their first booster vaccination in Study 700401 (which they received at 3 years after their third vaccination).

Those 29 subjects who were administered the first booster vaccination at 4 years after their third vaccination in Study 700401, will enter the current study in 2010. For these subjects the first visit will be shifted to take place at approximately 34 months after their first booster vaccination.

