### 9.2 Exclusion Criteria

Subjects who participated in Study 700401 and meet ANY of the following criteria are not eligible for participation in this study:

- Subject received any TBE vaccination since his/her first booster vaccination in Study 700401;
- Subject has a history of infection with or vaccination against other flaviviruses (e.g., Dengue fever, yellow fever, Japanese B encephalitis) since his / her first booster vaccination in Study 700401;
- Subject is known to be HIV positive (a special HIV test is not required for the purpose of the study) since his/her first booster vaccination in Study 700401;
- Subject received a blood product or immunoglobulins within 90 days before any blood draw or in the period between the blood draw and the booster vaccination (as applicable);
- Subject has a known or suspected problem with drug or alcohol abuse (> 4 liters of wine/week or equivalent level of other alcoholic beverages);
- Subject / parent(s) / legal guardian(s) is / are in a dependent relationship with the study investigator or with a study team member. Dependent relationship includes close relatives (i.e., children or grandchildren, partner / spouse, siblings) as well as employees of the Investigator or the site conducting the study.

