### 13.2 Datasets and Analysis Cohorts

Per-protocol dataset: Subjects will be included in the “per protocol” dataset if they

- fulfill inclusion/exclusion criteria
- have no major protocol violations
- have available serology data

Modified intent to treat dataset: Subjects will be included in the modified “intent to treat” analysis if they

- have available serology data

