4. ANALYSIS SETS

4.1. Full Analysis Set

An All-Enrolled Population will be defined as the Full Analysis Set, which consists of all subjects enrolled into the study. Any subjects who consented are included in the population. Subject disposition, history of tick bites, and demography will be presented for this population.

4.2. 'Per Protocol' Analysis Set

This analysis set is the primary analysis population for immunogenicity.

This Per-Protocol population includes subjects who:

1. Have been enrolled (consented) and meet all inclusion/exclusion criteria at all visits.
2. Have available assay results (ELISA or NT) at any blood sampling visit.
3. Have no other major protocol violations.

Above listed items 1 & 2 will be determined by computerized checks of the data, while item 3 will be determined by clinical review as these are considered as major protocol violations per the original protocol, which will eventually be entered into the database from Protocol Deviation (PD) case report form entries.

Subjects with major protocol deviations will be excluded from the primary analysis population, or in some instances, the ELISA and NT results affected by a protocol deviation at certain visit(s) will be excluded from the analysis.

If a subject meets the exclusion criterion 2, which is that subject has a history of infection with or vaccination against other flaviviruses (eg, Dengue fever, yellow fever, Japanese B encephalitis) since his/her first booster vaccination in Study 700401, the subject's affected ELISA results will be excluded from the analysis due to cross-reactivity. There is no cross-reactivity with the NT, so the NT results will be included in the analysis. The subject will be included in Per-Protocol population, under condition that he/she satisfies the rest of the conditions in above items 1 to 3.

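### Does SAP 6.4.4.1 remove from the per-protocol set a subject whom SAP 4.2 keeps in it?

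*SAP*

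**What the plan says.** Three texts bear on who belongs to the per-protocol set.

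- Protocol 13.2 admits subjects who "fulfill inclusion/exclusion criteria", have no major protocol violations and have serology data. It names no exception.
- SAP 4.2 defines the set and makes it the primary population for immunogenicity. Item 1 asks that subjects "Have been enrolled (consented) and meet all inclusion/exclusion criteria at all visits". The section then allows that, in some instances, only "the ELISA and NT results affected by a protocol deviation at certain visit(s) will be excluded from the analysis". It closes with a rule for exclusion criterion 2. Affected ELISA results are dropped because of cross-reactivity. For NT it says: "There is no cross-reactivity with the NT, so the NT results will be included in the analysis". On membership it says: "The subject will be included in Per-Protocol population, under condition that he/she satisfies the rest of the conditions" of items 1 to 3.
- SAP 6.4.4.1, on deviations assessed before enrollment, says: "Any subjects who do not meet the inclusion / exclusion criteria will not be included in the per-protocol immunogenicity population". It does not refer back to 4.2.

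The criterion itself, in Protocol 9.2, reads in part: "Subject has a history of infection with or vaccination against other flaviviruses", counted from the first booster in Study 700401.

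**The concern.** Criterion 2 looks back a long way. Protocol 6.3 enrolls most subjects "at approximately 38 months after their first booster vaccination in Study 700401", and 29 subjects at about 34 months. A yellow fever vaccination in that interval would mean the criterion was already met when the subject consented, and this is the situation 6.4.4.1 addresses. For such a subject 6.4.4.1 says out, with neither assay used, while 4.2 says in, with NT used. The SAP states no order of precedence, and Protocol 13.2 on its face agrees with 6.4.4.1.

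The per-protocol set carries the primary endpoint, NT seropositivity. SAP 4.2 has items 1 and 2 settled by computerized checks, so two programmers might in principle build different primary sets.

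Two wording points add to the impression of looseness. Item 1 of 4.2 seems to remove a whole subject for a failure at any visit, while a later sentence allows removal of results visit by visit. SAP 6.1 and 6.4.4.2 also refer to an evaluable immunogenicity population, which Section 4 does not define.

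**Working it through.** **Which rule an analyst would apply.** The subject in question met criterion 2 before enrollment and otherwise complied.

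| Source | In the per-protocol set? | NT | ELISA |
|---|---|---|---|
| SAP 4.2, item 1 alone | no | – | – |
| SAP 4.2, item 1 with its exception | yes | kept | affected results dropped |
| SAP 6.4.4.1 | no | – | – |
| Protocol 13.2 | no | – | – |

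Section 6.4.4.1 says the same as item 1 of 4.2 without its exception. Within 4.2 the exception is expressly carved out of items 1 to 3, because the subject must meet the rest of those conditions. A restatement of item 1 elsewhere does not cancel that. The revision table in SAP Section 1 records that version 1.1 specified the criterion 2 handling in 4.2 to match the protocol deviation plan, so the exception is deliberate.

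**Whom the conflict can reach.**

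1. Protocol 10.1 counts a person as enrolled on signing consent.
2. Protocol 10.3.2.1 lists the eligibility check ahead of the blood draw at Visit 1, and Protocol 9.2 makes a subject who meets criterion 2 ineligible.
3. A subject found ineligible and not bled has no assay result, fails item 2 of 4.2, and is out under every reading.
4. Flavivirus events after enrollment are outside 6.4.4.1, and 4.2 governs them.

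That leaves a subject who already met criterion 2 and was bled anyway. The documents neither report nor exclude such a subject.

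**Size if such subjects exist.** Inputs: n = 179 enrolled (SAP 2.2.2), used here as an upper stand-in for the per-protocol denominator, which is not given; and a rate near 90%, the planning value in Protocol 13.1, taken as 161/179 = 89.94%. With p = r/n, dropping one positive shifts the rate by −(1 − p)/(n − 1), and dropping one negative by +p/(n − 1).

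| Dropped (assumed) | Rate | Shift (points) |
|---|---|---|
| 1 positive | 160/178 = 89.89% | −0.06 |
| 1 negative | 161/178 = 90.45% | +0.51 |
| 3 positives | 158/176 = 89.77% | −0.17 |
| 3 negatives | 161/176 = 91.48% | +1.53 |

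At the planned n = 175, the most one subject can move the rate is 1/175 = 0.57 points (174/175 to 174/174). With a denominator of 90 and 81 positives (assumed), dropping one negative gives 81/89 = 91.01%, a shift of +1.01 points.

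For comparison, the exact 95% interval for 161/179 runs from 84.57% to 93.93%, which is 5.4 points below the estimate and 4.0 above. The one-subject shift of 0.51 points is about a tenth of the lower arm. Three negatives is an extreme case: at 90% seropositivity and with independence its chance is 0.1³ = 0.1%.

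**The case for a change.** The strongest case for a change is that a primary analysis set should be derivable in only one way. The SAP states no precedence, and a programmer checking against Protocol 13.2 could settle on exclusion. Nor does the mITT analysis cover everything: the logistic regression, the reverse cumulative curves and the extrapolated seropositivity and GMT estimates are per-protocol only, and a dropped subject takes any extrapolated later values along. An exception clause in 6.4.4.1 would cost almost nothing.

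The textual mismatch stands, and so does the limit on mITT as a backstop. What does not follow is that the mismatch would lead analysts astray. A set is built from the section that defines it, and that section addresses this criterion by name. SAP Section 2 also says that programming rules are prepared separately; their content is not available here, so divergent derivations are possible but not shown.

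The wording points are weaker. In 6.1 the evaluable immunogenicity population can only be the set in 4.2: 4.2 calls its set primary for immunogenicity, 6.1 adds mITT as a further analysis, and 6.1 limits the regression to the per-protocol population. That is a slip in terms. On whole-subject against visit-level exclusion, 4.2 allows both and leaves major violations to clinical review. A fixed rule that any criterion first failed after Visit 1 costs only the affected results would be a new choice. It would loosen item 1, sit uneasily with 6.4.4.2, and still need separate provision for other late failures such as outside TBE vaccination.

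**Conclusion.** The sections differ in wording, but no change to the plan is called for. This is a missing cross-reference that an analyst fills from 4.2, the defining, specific and deliberately revised text. The affected case is narrow and not shown to occur. If it did, one subject would move the primary NT rate by −0.06 to +0.51 points on 179 subjects at about 90%, and by about 1 point if the denominator were half that. These figures assume the planning rate and a denominator near full enrollment.

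The study is descriptive with no hypothesis or decision rule (SAP 5.1), so no conclusion turns on a shift of that order. Either handling gives a defensible per-protocol estimate: keeping the subject rests on the SAP's statement that NT does not cross-react, and removing the subject is the stricter reading in Protocol 13.2. The mITT seropositivity rates and GMTs are the same under both. The judgement would need another look only if a substantial number of subjects had been bled with the criterion already met, and nothing in the documents suggests that.
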